Hemostatic effect is determined by dose of oxymetazoline instilled by the surgeon.

Methods:

Thirty patients of [name] who will undergo functional endoscopic sinus surgery, turbinate surgery or adenoidectomy and are anticipated to receive oxymetazoline-soaked pledgets for hemostasis will be enrolled.

Patients ages 2 through 18 yrs. will be enrolled if they are scheduled for

- 1) Functional endoscopic sinus surgery (ten patients)
- 2) Turbinate reduction (with or without tonsillectomy and/or adenoidectomy) (ten patients)
- 3) Adenoidectomy (ten patients)

Patients will be excluded if they have been treated with oral decongestants or antihistamines within 24 hours of surgery, are taking anticoagulants, have a history of nasal trauma within past 3 months, have a history of epistaxis within past 3 months, have a history of hypertension or cardiac disease, or are allergic to oxymetazoline.

There will be no change in the conduct of the general anesthetic care related to the study protocol. Our usual practice will be followed. For premedication, midazolam (0.5 mg/kg to a maximum of 15 mg) will be administered 15-45 minutes prior to the procedure at the discretion of the attending anesthesiologist. An inhalation induction with sevoflurane or an intravenous induction with propofol will be performed by the attending anesthesiologist and titrated to attempt to maintain the bispectral index (BIS) between 40 and 60 to ensure adequate and similar depth of anesthesia. It will not be considered a protocol violation if the BIS is not maintained at this level. Fluid will be administered to

attempt a total of 15 ml/kg for procedures less than 1 hr or maintenance plus replacement for procedures greater than 1 hr. It will not be considered a protocol violation if this amount of fluid is not infused.

Blood pressure and heart rate and will be recorded at 5 min intervals until discharge from PACU or final blood draw, whichever comes first.

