The surgeon will place oxymetazoline-soaked pledgets according to usual practice. [name] will make two different observations to assess the amount of bleeding and ease of hemostasis (10)

- 1) A four point scale to record subjective bleeding following removal of pledgets

- 0= none, 1= minimal/restricted, 2=moderate/diffuse ooze, 3=severe/brisk
- 2) A six point scale to assess ease of hemostasis
1=very easy, 2=easy, 3=usual, 4=some effort required, 5=difficult, 6=extremely difficult

Blood pressure and heart rate and will be retrieved from EPIC for analysis

Prior to the study Drs. [name] & [name] determined that 10 pledgets in 15 ml of oxymetazoline (1.5 ml per pledget) provided the necessary amount of oxymetazoline for clinical use. The number of pledgets placed will be recorded at the time of insertion. If placement is separated by greater than five minutes, then this will be recorded as a separate event. The volume at each time point and the total dose will be recorded. Age-matched, procedure matched control patients not receiving oxymetazoline will be used for comparison. We will do a retrospective chart review of the control patients for hemodynamic parameters.

Statistical Analysis:

Compare the incidence of hypertension using systolic blood pressure and mean arterial pressure criteria using age adjusted normative tables

Compare the incidence of bradycardia defined as HR < 60 bpm, or tachycardia defined as HR>100

Compare the use of vasodilators for the treatment of hypertension

Compare the use of atropine/glycopyrrolate for the treatment of bradycardia

Compare the volume of oxymetazoline instillation and hemodynamic changes

Measure the serum level of oxymetazoline at approximately 5 (3-6 min), 10(8-12 min), 20(18-22 min), 45 (30-60 min), 90 (75-120 min) and 150 (135-240 min) minutes using the protocol specified above.

Compare the degree of bleeding and the ease of hemostasis using the subjective rating scale by the single surgeon observer.

All demographic and parametric data will be presented as mean (\pm SD). Normally distributed interval data will be analyzed using unpaired t-test. Nominal or ordinal data will be analyzed using Chi-squared contingency table or a Fisher's exact test with Yates correction factor. A $P < 0.05$ will be used to express statistical significance.

REFERENCES:

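### Heart-rate events are counted against one fixed pair of limits for ages 2 to 18; add an age-adjusted, windowed heart-rate comparison and reference the counts to age, as is done for blood pressure

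*Combined protocol and SAP*

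**What the plan says.** All places are in the combined protocol and SAP.

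- **Statistical Analysis, heart rate:** "Compare the incidence of bradycardia defined as HR < 60 bpm, or tachycardia defined as HR>100". No age-referenced or baseline-referenced definition is given.
- **Statistical Analysis, blood pressure:** the preceding item judges hypertension by systolic and "mean arterial pressure criteria using age adjusted normative tables".
- **Methods, population:** "Patients ages 2 through 18 yrs. will be enrolled if they are scheduled for" one of three procedures, ten patients each, 30 in all.
- **Methods, data:** blood pressure and "heart rate and will be recorded at 5 min intervals", and later "Blood pressure and heart rate and will be retrieved from EPIC for analysis".
- **Methods, controls:** "Age-matched, procedure matched control patients not receiving oxymetazoline will be used for comparison", and "We will do a retrospective chart review of the control patients for hemodynamic parameters". Their number is not stated.
- **Statistical Analysis, general rule:** "Normally distributed interval data will be analyzed using unpaired t-test". It is not assigned to heart rate and has no age term.

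Specific Aims/Objectives names heart rate beside blood pressure in the primary objective; the Hypotheses name only a rise in blood pressure. Background and Significance cites a paediatric study in which heart rate fell over about ten minutes following application, and an adult study with a small fall. Neither is given a size.

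**The concern.** Two neighbouring outcomes in the same children are handled differently, and no reason is given. A limit of 60 is close to the usual rate of a patient whose untreated rate is low and far from that of a patient whose rate is high. If rate falls with age, the same slowing is counted in an adolescent and missed in a toddler, while a toddler may exceed 100 with no drug effect. The background makes slowing the heart-rate effect to look for, yet the only named between-group heart-rate comparison is these two counts. A null result on them could be read as no effect when the measure could hardly have shown one. The plan also does not say how a series of 5-minute readings becomes one event per patient.

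**Working it through.** **Nothing to reproduce.** The documents give no heart-rate level, SD, effect size, number of readings, number of controls or power. From the documents: limits 60 and 100, ages 2 to 18, 30 treated patients, 5-minute readings, alpha 0.05. Everything else is assumed.

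**Step 1. Fall needed to cross 60.** From 80: 80 - 60 = 20 bpm (25%). From 100: 40 bpm (40%). From 120: 60 bpm (50%).

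**Step 2. Chance that a single reading crosses a limit**, Normal with SD 12, using Φ((60 - mean)/12).
- Mean 112 (assumed, age 2): z = -52/12 = -4.33, practically never. After a 10 bpm fall, z = -42/12 = -3.5, about 0.02%.
- Mean 75 (assumed, age 18): z = -15/12 = -1.25, about 11%. After the fall, z = -5/12 = -0.42, about 34%.
- Above 100 with no drug at mean 112: z = (100 - 112)/12 = -1, so about 84% of readings.

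**Step 3. Patients aged 2-6 with any reading past the limit** (12 or 24 readings, simulated).

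| Assumed mean, age 2 to 18 | <60, no drug | <60, sustained 10 bpm fall | >100, no drug |
|---|---|---|---|
| 112 to 75 | about 0.1% | 0.6-2% | 91-99.6% |
| 105 to 72 | 0.2-0.8% | 3-8% | 78-98% |
| 100 to 70 | 0.8-2.5% | 6-18% | 65-93% |

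The loss at the youngest ages is near total on the first line and moderate on the last.

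**Step 4. Power over ages 2-18.** There were 18 scenarios: the three age lines, three between/within-patient SD splits (11/5, 10/7, 8/9; total SD about 12), and 12 or 24 readings. Design: 30 v 30, exact age matching, uniform ages, two-sided 0.05. Tests: Fisher's exact for counts, unpaired t-test for raw means, linear model with group and age. Ranges are over scenarios, with simulation error of one to two points.

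Sustained fall of 10 bpm:
- <60 count: 10-56%
- >100 count: 32-53%
- raw mean heart rate: 76-96%
- mean heart rate with age as covariate: 92-100% (null rejection 4-6%)

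Sustained fall of 5 bpm, in the same order: 1-10%, 5-10%, 16-30%, 39-65%.

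Fall of 10 bpm in the first two readings only (10 minutes / 5 minutes = 2):
- <60 count: 1-6%
- whole-record mean, age-adjusted: 4-12%
- lowest reading, age-adjusted: 12-42%
- mean of those two readings, age-adjusted: 90-96%

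**Step 5. Hand check of the means.** The SD of a patient mean over k readings is √(between² + within²/k). The standardised shift is d = shift/SD, and 30 v 30 needs d of about 0.72 for 80% power.
- Sustained fall, split 11/5, k = 12: SD = √(121 + 25/12) = 11.1, d = 0.90.
- Two-reading fall, whole record: the shift dilutes to 10 × 2/12 = 1.7 bpm (k = 12) or 10 × 2/24 = 0.8 bpm (k = 24). On the 11/5 split d is 0.15 or 0.08.
- Two-reading fall, two-reading window: SD = √(121 + 25/2) = 11.6, d = 10/11.6 = 0.87.

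The ordering follows from dilution alone.

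**Step 6. Marked slowing in a few.** If 25% of treated patients fall 40 bpm for two readings, <60 has 13-32% power and the windowed age-adjusted mean 59-72%. The whole-record age-adjusted mean has 5-12%, below the count.

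**Step 7. Does an age-referenced limit help in itself?** A low limit tuned to the same drug-free event rate as <60 gains 19-47 points for a sustained 10 bpm fall. That is a favourable case, because the true age means are known. A limit 30 bpm below the age mean gives only 14-73%. In a simpler model (one value per patient, mean 95 to 65, SD 15), an age-specific 5th percentile does worse than <60: 13% v 21%.

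**Step 8. Event rule.** On the 112 to 75 line, drug-free <60 incidence over ages 2-18 is 5-14% if any reading counts, 2-3% if two consecutive readings are needed, and 0-1% on the patient's mean.

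**The case against.** **Controls are age-matched.** This stands as far as bias goes. A reader might infer that the fixed limits bias the treated-control comparison; with close matching the documents do not support that. Matching cannot restore sensitivity where both groups are far from 60 or already above 100.

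**Heart rate is not confined to the two counts.** The general t-test sentence could be applied to it, and the plan also relates instilled volume and plasma concentration to hemodynamic changes. This is partial mitigation: none of these is an age-adjusted group comparison, and the raw t-test loses power by ignoring age (16-30% v 39-65% at 5 bpm).

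**The large power gap needs a sustained fall.** This stands. A reader might infer that averaging the whole record with an age term is enough. The cited paediatric finding concerns the early minutes, and under that pattern the whole-record mean largely fails too.

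**Counts answer a safety question that a mean does not.** This also stands. The background raises serious cardiovascular effects, so the counts should be kept. Drug treatment of bradycardia, which the plan records, would also raise later readings and dilute a long average.

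**Age-specific limits can do worse.** True in some settings, including adolescents with low resting rates, so superiority in every setting should not be claimed.

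**Conclusion.** The point holds as a cheap improvement of minor to moderate severity. The differing treatment of heart rate and blood pressure is plain in the text. The loss of sensitivity rests on one assumption the documents cannot confirm, that untreated heart rate is higher in younger children. Its size rests further on the assumed levels, SD, number of readings, 30 controls and shape of the fall, so the percentages compare methods and do not forecast this trial. Within those inputs the windowed age-adjusted comparison beat the <60 count in every pattern tested. A gain for the whole-record mean appears only if slowing persists.

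A reader might go further and infer that the heart-rate results would be invalid, or that 60 and 100 are clinically wrong. The documents support neither: the stated hypothesis concerns blood pressure, matching limits bias, and the point is about analysis definitions only. The missing one-event-per-patient rule affects the blood-pressure counts equally and adds no weight against the heart-rate limits as such.

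**What to change.** 1. Add a treated-control comparison of heart rate with age as covariate over a pre-specified early window. Controls have no instillation time, so start the window from an event that can be dated in both groups. The window must cover instillation in treated patients without being much longer than needed: two affected readings in a window of four halve a 10 bpm shift to 10 × 2/4 = 5 bpm. Each patient's lowest reading is an alternative needing no window, but is weaker for a brief fall (12-42%). Do not rely on the whole-record mean alone.
2. Keep the bradycardia and tachycardia counts as a safety comparison, with age-referenced limits fixed by the investigators before the data are seen, in line with blood pressure.
3. State how the 5-minute readings form one event per patient, identically in both groups.

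These are analysis definitions, not treatment triggers.

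Cost: a few lines of definition and one regression, with no new data provided the control charts hold readings at a similar interval. Downsides: a little more analysis work, the need to settle window and anchor in advance, and less comparability with reports using 60 and 100. Awake norms may also not fit anaesthetised children; that affects the age-referenced counts but not the covariate analysis, which needs no norm table.

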Giannakopoulos studied the cardiovascular effects and pharmacokinetics of an intranasal 3 percent tetracaine/0.05 percent oxymetazoline spray at two different dose levels in adult dental patients. (8) A small decrease in heart rate and a small increase in diastolic blood pressure was noted. Serum levels of oxymetazoline were measured and a half-life of 1.72 to 2.32 hours was noted. No similar pharmacokinetic studies have been reported in children. Latham and Jardine reported oxymetazoline-induced hypertension in a 4-year-old child. (9) They also sought to investigate alterations in the amount of medication delivered based on the delivery method. There was up to a 75-fold increase in the volume of medication administered when the bottle was held inverted. Squeezing the bottle in the upright position resulted in a mist with the delivery of $28.9 \pm 6.8 \mu\text{l}$ of fluid. The amount delivered was effort independent. When the bottle was inverted and squeezed, the volume administered was effort dependent.

Current practice at NCH is to soak nasal pledgets with full strength oxymetazoline and insert a varying number of pledgets on the nasal turbinates or into the sinuses for hemostasis, or on the adenoid bed.

This proposed study will assess the hemodynamic effects and measure the systemic absorption of topically applied oxymetazoline in patients undergoing functional endoscopic sinus surgery, turbinate surgery, or adenoidectomy.

Specific Aims/Objectives:

The primary objective is to determine the perioperative hemodynamic effect of oxymetazoline applied topically for vasoconstriction in patients undergoing functional endoscopic sinus surgery, turbinate surgery or adenoidectomy using blood pressure and heart rate intraoperatively (OR) and postoperatively (PACU) until discharge from phase 1 of the PACU.

A secondary objective is to measure the plasma concentrations of oxymetazoline at discrete time periods from instillation and correlate with hemodynamic effects, as well as determine the rate of decline in levels as a function of time.

A secondary objective is to assess the degree of bleeding and ease hemostasis rated by a single observer to minimize variability.

Hypotheses:

Instilled oxymetazoline causes an increase in blood pressure in the intraoperative and postoperative period and, though absorption is rapid and variable, effects are related to serum level of oxymetazoline.

The decline in hemodynamic effect and serum levels is a function of time.

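### The dose–hemostasis hypothesis has no stated analysis; the rule given for ordinal scores ignores their order, and no stated test allows for procedure

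*Combined protocol and SAP*

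**What the plan says.** The Hypotheses section ends with "Hemostatic effect is determined by dose of oxymetazoline instilled by the surgeon". The matching objective in Specific Aims/Objectives does not mention dose: "A secondary objective is to assess the degree of bleeding and ease hemostasis rated by a single observer to minimize variability".

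Methods enrols ten patients in each of three procedures and leaves pledget placement to the surgeon's usual practice. On dose it says "If placement is separated by greater than five minutes, then this will be recorded as a separate event" and "The volume at each time point and the total dose will be recorded". Bleeding is scored 0–3 after the pledgets are removed. Ease of hemostasis is scored 1–6, with no time given. The chart review of controls covers hemodynamic parameters only.

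In Statistical Analysis, the one comparison that uses dose is "Compare the volume of oxymetazoline instillation and hemodynamic changes". The scores appear in "Compare the degree of bleeding and the ease of hemostasis using the subjective rating scale by the single surgeon observer", which names no comparator. Two test rules follow: "Normally distributed interval data will be analyzed using unpaired t-test" and "Nominal or ordinal data will be analyzed using Chi-squared contingency table or a Fisher's exact test with Yates correction factor".

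**The concern.** Both sides of the hypothesised relation are recorded, but the plan does not say how they will be related. The test, the dose measure (first placement or total) and any grouping of doses or scores are left to be chosen after the data are seen.

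The stated rules do not settle this well. Chi-squared and the usual Fisher test treat a 0–3 or 1–6 score as unordered labels. The t-test could compare volume between low and high scorers, but no cut is given. None of these tests separates the three procedures, and a sinus operation and an adenoidectomy may differ both in pledgets used and in bleeding. Total dose may also include pledgets placed later because the patient was bleeding. Depending on these choices, a real relation could be missed or masked, or a spurious one reported.

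**Working it through.** **Inputs from the documents.** 10 + 10 + 10 = 30 treated patients; 15 ml / 10 pledgets = 1.5 ml per pledget; scores with 4 and 6 ordered levels; significance level 0.05 (sidedness is not stated; two-sided assumed). The plan gives no power, effect size or dose spread, so there is no figure of its own to reproduce.

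**1. Hypothesis against the analysis list.**

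| Statistical Analysis line | Uses volume? | Uses a score? |
|---|---|---|
| Volume and hemodynamic changes | yes | no |
| Bleeding and ease of hemostasis | no | yes |
| All other lines | no | no |

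No line has both. Controls received no oxymetazoline and have no planned scores, so any contrast of scores must lie within the 30 treated patients.

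**2. Does the named test use order?** Take an invented table of three dose groups of 10 by the 4-point score, with rows (1,3,4,2), (2,4,3,1), (4,3,2,1). Column totals are 7, 10, 9 and 4, so the expected counts in each row are 2.33, 3.33, 3 and 1.33. Chi-squared = Σ(O − E)²/E = 2.000 + 0.200 + 0.667 + 0.500 = 3.367 on 6 df, P = 0.762. Shuffling the score columns leaves this unchanged, while Spearman's coefficient moves from −0.30 (P = 0.11) to 0.05 (P = 0.79). The named test carries no information on order.

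**3. Cell counts.** Dose thirds by the 4-point score: 30/12 = 2.5 expected per cell. By the 6-point score: 30/18 = 1.7. The chi-squared approximation is weak at these counts.

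**4. Power (assumed inputs).** Assume log-odds of 0.6 per SD of dose.
- Chi-squared on dose thirds: 9–18%.
- Rank test within procedure: 33–36%.
- t-test of volume at a mid-scale score split (2–8 pledgets equally likely, evenly filled score categories): 34%, against 34–36% for the rank test in the same run.
- t-test over all possible splits: 21–35% with evenly filled score categories, 4–33% with skewed ones. Choosing the best split afterwards rejects in 12–18% of trials when dose has no effect.

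**5. Procedure (assumed inputs).** Dose has no effect, but procedure shifts both dose and bleeding.
- Unstratified rank test: rejects in 9–31%.
- Rank test within procedure: 4–5%.
- Unpaired t-test, in a run with shifts of 1–2 pledgets and 0.5–1.0 log-odds per step: 6.5–28%.

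If both shifts go the same way, the false signal is that more volume goes with worse scores, so a true benefit can be masked. In a separate run with a true effect of 0.75 latent SD per SD of dose and shifts of 1 SD per step, on the 4-point scale, Spearman had 36% power and the stratified test 83%.

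**6. Which volume?** Dose has no effect, but 25–100% of patients rated in the upper half of the scale then receive 1–2 more pledgets. The stratified test rejects in 6–48% using total volume and in 4–5.5% using first-placement volume. Counting all pledgets placed before the rating does not remove the problem. The ease rating has no stated time and could follow the repeat pledgets; under that assumption the rejection rate was 4–46%, against about 5% for first-placement volume.

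**7. Precision at n = 30.** Use Fisher's z with two degrees of freedom spent on procedure: SE = √((1 + r²/2)/25).
- r = 0: SE = 0.200; tanh(±1.96 × 0.200) gives −0.37 to 0.37.
- r = 0.3: z = 0.310, SE = 0.204; 95% CI −0.09 to 0.61.
- Correlation detectable with 80% power, by the simpler approximation with SE = 1/√25: tanh((1.960 + 0.842)/√25) = 0.51.

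**The case against.** **The gap is partly one of wording.** With no control scores, dose is the natural comparator for the bleeding and hemostasis line, and the authors may have meant it. That is fair, and it rules out the stronger reading that the plan has dropped the hypothesis. Even so, the test, the dose measure and any grouping remain unstated.

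**The plan's own t-test does as well.** At a mid-scale split it does, so a reader should not infer that the stated methods must be badly underpowered. The shortfall belongs to chi-squared on dose groups and to extreme splits. What the t-test lacks is a stated split and any allowance for procedure.

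**Controls are procedure-matched.** This does not help. Matching serves the hemodynamic comparison and cannot balance dose across procedures among treated patients.

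**Every magnitude is assumed, and the stakes are modest.** This stands. The procedure and repeat-placement biases run from negligible to large over the assumed settings, and the documents do not show that either will occur. The question is secondary, dose is the surgeon's choice, there is one rater, and two scores will be tested. An exploratory label with an estimate and interval is the right level of ambition, and the exact permutation or bootstrap recipe is a matter of preference.

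**Conclusion.** The point holds on the text: a stated hypothesis has no stated analysis, the rule for ordinal data discards order, and no stated test includes procedure. It should be corrected, but it does not threaten the primary objective.

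The size of the effect is illustrative only. On the assumed inputs, the gain over chi-squared on dose groups is material, roughly a doubling of power or more, and stratifying keeps the false-positive rate near 5%. There is no real gain over a mid-scale t-test. The main benefit is an analysis fixed in advance that can be interpreted.

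Two further inferences are not supported. The documents do not show that procedure will bias the result: that needs both dose and bleeding to differ by procedure, which they do not quantify. And attaching Yates' correction to an exact test is a wording slip, not evidence that an invalid test will be run.

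**What to change.** Add to Statistical Analysis:

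> Each score will be compared with the volume of the first pledget placement event by a rank correlation stratified by procedure (for example, ranks centred within procedure, with a P value from permuting scores within procedure), reported with a 95% confidence interval. Total volume will be shown as a sensitivity analysis, because later pledgets may be placed in response to bleeding. The analysis is exploratory: dose is chosen by the surgeon, so an association does not show that dose determines hemostasis, and a null result in 30 patients is inconclusive.

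Use first-placement volume for both scores. Reserve chi-squared and Fisher's exact tests for nominal and binary data, and delete the reference to Yates' correction from the exact test.

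The cost is a few sentences. Volumes by placement event and both scores are already to be recorded, and treatment does not change. There are two downsides. If procedure does not matter, stratifying loses about 4–10 percentage points of power on the assumed inputs, depending on the rank statistic. First-placement volume also understates dose when more pledgets follow.

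### No comparison is named as the test of the primary objective or of the blood pressure hypothesis; six hemodynamic comparisons share one unadjusted P<0.05, and blood pressure is compared with controls explicitly only as a yes/no incidence

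*Combined protocol and SAP*

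**What the plan says.** Under Specific Aims/Objectives, "The primary objective is to determine the perioperative hemodynamic effect of oxymetazoline applied topically for vasoconstriction", "using blood pressure and heart rate intraoperatively (OR) and postoperatively (PACU) until discharge from phase 1 of the PACU". No variable, time window or summary measure is singled out. Under Hypotheses the direction is given: "Instilled oxymetazoline causes an increase in blood pressure in the intraoperative and postoperative period".

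The Statistical Analysis does not link that hypothesis to a test. Its first item reads "Compare the incidence of hypertension using systolic blood pressure and mean arterial pressure criteria using age adjusted normative tables". Its second reads "Compare the incidence of bradycardia defined as HR < 60 bpm, or tachycardia defined as HR>100". It goes on to vasodilator use, atropine or glycopyrrolate use, oxymetazoline volume against hemodynamic changes, and the bleeding and ease-of-hemostasis ratings.

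On methods it states "Normally distributed interval data will be analyzed using unpaired t-test" and "Nominal or ordinal data will be analyzed using Chi-squared contingency table or a Fisher's exact test with Yates correction factor". One threshold, P<0.05, "will be used to express statistical significance" throughout. There is no ranking of comparisons, no adjustment and no exploratory label.

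Thirty treated children are planned, ten per procedure type. Controls are matched on age and procedure and taken from chart review for hemodynamic data. Their number is not stated, and there is no power calculation.

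**The concern.** Two things follow from the missing primary comparison.

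First, a P value below 0.05 on any of several hemodynamic outcomes, in either direction for heart rate, could be presented as the effect that the primary objective seeks. The stated 0.05 then does not describe the chance of a false primary claim. The number of tests is also open: readings come every 5 minutes, in two settings and three procedure groups, and no rule says how they are reduced to one value per child.

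Second, the hypothesis concerns a rise in pressure, a continuous quantity, but the comparison written down for it counts children above a cut-off. That discards information in a study of 30 treated children, so a real rise could well be missed.

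**Working it through.** **The plan's own figure.** The sample size of 30 cannot be reproduced, because no effect size, SD, event rate, power or control number is given. The only error rate stated is 0.05 per test.

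**Counting the comparisons** (Statistical Analysis):

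| Comparison | Count | Treated v control, primary objective? |
|---|---|---|
| Hypertension, by systolic and by mean pressure | 2 | Yes |
| Bradycardia; tachycardia | 2 | Yes |
| Vasodilator use | 1 | Yes |
| Atropine/glycopyrrolate use | 1 | Yes |
| Volume v hemodynamic changes | 1 | No: controls received none, so within treated children |
| Bleeding; ease of hemostasis | 2 | No: secondary objective, no control ratings planned |

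That makes nine in all, six of which bear on the primary objective against controls.

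**Nominal false-positive risk.** For k independent tests at 0.05 the risk is 1 − 0.95^k.

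- k = 6: 1 − 0.95^6 = 0.265. The upper bound under any dependence is 6 × 0.05 = 0.30.
- k = 9: 1 − 0.95^9 = 0.370. The upper bound is 9 × 0.05 = 0.45.

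Simulated two-sided normal tests with an assumed equal correlation (400,000 draws) give, for six tests, 0.24, 0.21 and 0.14 at correlations of 0.3, 0.5 and 0.8. For nine tests they give 0.33, 0.27 and 0.17.

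**Risk with the tests the plan names.** The six outcomes are yes/no, so the actual size depends on the test. Exact enumeration at an assumed 30 v 30, then 1 − (1 − size)^6:

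| Event rate (assumed) | Fisher or Yates size | Six tests | Uncorrected chi-squared size | Six tests |
|---|---|---|---|---|
| 5% | 0.0015 | 0.009 | 0.0284 | 0.159 |
| 10% | 0.0094 | 0.055 | 0.0544 | 0.285 |
| 20% | 0.0222 | 0.126 | 0.0490 | 0.260 |
| 50% | 0.0274 | 0.154 | 0.0519 | 0.274 |

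The plan allows both chi-squared and Fisher's test and does not say when each applies.

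**Cost of the yes/no outcome.** Assumptions: 30 v 30, two-sided 0.05, normal pressures with equal SD.

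1. The unpaired t-test has 80% power at a difference of 0.736 SD.
2. If 10% of controls are hypertensive, the cut-off lies 1.282 SD above the control mean. After a 0.736 SD shift it lies 1.282 − 0.736 = 0.546 SD above the treated mean, so about 29% of treated children are hypertensive.
3. Exact power for 10% v 29% is 0.35 with Fisher's test and 0.47 with uncorrected chi-squared.
4. The same steps at control rates of 5%, 20%, 30% and 50% give treated rates of 18%, 46%, 58% and 77%. Fisher power is then 0.18, 0.47, 0.51 and 0.48; uncorrected chi-squared gives 0.38, 0.57, 0.61 and 0.58.

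Across this range the yes/no comparison never reaches the 80% of the t-test.

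**The case against.** A reader might infer from nine tests at 0.05 that a chance finding of an oxymetazoline effect is likely. The documents do not support that. Nine tests at 5% cannot exceed 45%, and three of the nine cannot supply a false primary claim against controls. Several of the remaining six are closely related, such as systolic and mean pressure, or bradycardia and the drugs given for it, which lowers the figure. Fisher's test or the Yates correction lowers it further: with 10% events the six-test risk is about 5.5%, hardly above nominal. The count of six is itself a reading. Taken as written bullets there are four, with a nominal risk of 1 − 0.95^4 = 18.5%. Testing the operating room and recovery separately would raise the risk, but the plan specifies no such split. All of this stands, and it limits the multiplicity part of the point.

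A reader might also infer that continuous pressure will not be analyzed. That goes too far. The t-test sentence and the item on hemodynamic changes leave room for it. What is missing is a listed treated-versus-control comparison of pressure as a continuous measure.

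Finally, this is a small observational study with retrospective controls and no power claim, so a descriptive label would be defensible. But the plan states a directional hypothesis and a significance threshold, and it does not use that label.

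**Conclusion.** The point holds in a limited form. No comparison is designated as the test of the primary objective or of the hypothesis that pressure rises, and one unadjusted P<0.05 covers everything. For the six relevant comparisons the nominal risk of at least one false positive is about 26% if independent, less with correlation. It is roughly 1 to 15% under Fisher's test and 16 to 29% under uncorrected chi-squared, at the assumed 30 v 30 and event rates of 5 to 50%. The risk is uncontrolled and undefined, but it is not shown to be high.

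The loss of power is the firmer part. A shift that a t-test detects with 80% power is detected with about 35% (Fisher) or 47% (uncorrected chi-squared) when reduced to hypertension yes or no, given 10% hypertension in controls. These figures rest on 30 controls, normal pressures and assumed event rates, none of which the documents give. The change should be made before analysis.

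**What to change.** In the Statistical Analysis, name one primary comparison tested at 0.05: the treated-versus-control difference in mean systolic pressure change from the last reading before instillation, averaged over a pre-specified window that covers the intraoperative and recovery periods named in the hypothesis. First pledget placement is time zero for treated children. Controls take a matched index time from the chart. A short window, such as the first 30 minutes, would be arbitrary and could miss recovery. The end of the window should follow the same rule in both groups, since recording in treated children may stop at the last blood draw.

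Report hypertension incidence, heart rate, drug use, volume and bleeding comparisons as secondary or exploratory, each with an estimate and 95% confidence interval.

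The costs are modest. Treated children already have pressures recorded every 5 minutes, and control pressures come from the planned chart review, so no new prospective data are needed. An index-time rule has to be written and applied to control charts, including how to handle treated children with placements more than five minutes apart. Other P values below 0.05 can no longer be presented as confirming the primary objective.
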